7. STUDY DESIGN

Please see Appendix A for study flow diagram.

This is a prospective randomised controlled study designed to assess the impact of specific training interventions on surgical trainee's operative performance and patient outcomes following primary elective THR. We will also study the performance and patient outcomes of both 'Experts' and 'Fellows' in an additional comparator group, which will allow a potential expert standard in THR to be defined.

All study participants will be recruited from 2 Hospitals within the Thames Valley (Oxford) Post-graduate Medical Deanery, and will be composed of: Trauma & Orthopaedic Specialty Registrars ('StRs') holding national training numbers; Consultant Orthopaedic Surgeons ('Experts'); and Orthopaedic Arthroplasty Fellows ('Fellows'). Over the 18-24 month anticipated study period we aim on recruiting a total of up to 16 StR's, 8 Fellows, and 5 Experts. See section 9 for further details on participant recruitment.

StR's will be randomised in a 1:1 ratio to receive either: routine normal Deanery training (the control group, n=8); or routine normal Deanery training with additional simulation-based and cognitive learning (the intervention group, n=8). The intervention group will receive this training for 1-2 hours per week over a 4 to 6-week period. The 'Experts' and 'Fellows' will not be eligible for any intervention, and will act as a separate comparator group.

All participants will be assessed intra-operatively at set timepoints when performing elective primary THR surgery on patients within the named NHS Hospitals. The timepoints will vary depending upon each group. Each StR enrolled into this study will be assessed at a minimum of 8 separate THR operations over a 6-month period, commencing at 6 weeks in to their 6-month clinical placement. Both the 'Fellows' and 'Experts' will be assessed at a minimum of 5 separate THR operations depending upon the reliability of their performance data.

All patients in this study will have been listed for routine elective primary THR surgery under a named Orthopaedic Consultant on the NHS. There will be no interventions or deviations from routine clinical practise regarding the pre-operative investigations or work-up, the operation itself, the peri-operative care, or post-discharge follow-up.

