The outcome measures will be surgeon-specific and patient-specific. These outcome measures for the 'Trainee' group will commence following completion of the simulation training (if applicable), whereas they can commence immediately following study approval for the 'Expert' group. The surgeon-specific outcome measures will be the objective motion-analysis metrics generated by validated and extensively used wireless sensors placed on the elbows of surgeons under their sterile gowns during the operation; and subjective assessments of surgical trainee performance using validated and reliable forms of structured human grading. Patient-specific outcome measures will be collected for a pre-determined number of patients who have undergone a primary elective THR by any of the surgeon participants in this study. All patient-specific outcome measures (with the exception of a post-operative questionnaire) are routinely collected as part of the patients NHS clinical care, and no other additional investigations are required for conducting this research. All patients will be asked to provide their written informed consent for the use of their data in this study. The patient-specific outcome measures include: pre- and post-operative blood tests and radiograph (X-ray) analysis; the incidence of blood transfusions and any other peri-operative complications; the in-patient length of stay; and two patient-reported outcome measure (PROMs) questionnaires.

Statistical analysis will then be performed on the data collected, specifically aiming to identify any significant differences in either surgeon performance metrics, or patient outcome measures between:

- 1) The StR's who have undertaken additional simulation training versus those who have routine Deanery training.
- 2) The 'Trainee' group and the 'Expert' group. A sub-group analysis may be performed within the 'Expert' group also to determine any differences between the Consultants and Fellows.

In summary, this novel research will use validated methodology and routinely collected patient outcome measures in order to determine the impact of simulation training on surgical trainee performance and patient outcomes following a primary elective THR, and also help to benchmark an expert level of performance in this commonly performed and highly effective operation. The results of this study will hopefully help in shaping the future of orthopaedic surgical training and assessment within the United Kingdom.

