6. OBJECTIVES AND OUTCOME MEASURES

Objectives	Outcome Measures	Timepoints of evaluation
Primary To assess the impact of simulation training on surgical trainee performance and patient outcomes following THR.	Participants: 
 Wireless motion data metrics from elbow worn sensors (hand movements, path length and time taken) Global Rating Scales (GRS). Objective Structured Assessment of Technical Skills (OSATS). Surgical checklists. Patients: 
 X-ray analysis of THR.[4] Blood loss and transfusion rates. Peri-operative patient morbidity In-patient length of stay. PROMs: EQ-5D and OHS. 	Intra-operative assessments to be performed at a minimum of 8 separate THR operations for each participant in Group 1 (StR'S) over a 6-month period. Outcome measures data will be collected for all patients who have had a THR performed by any participant as the lead surgeon in this study.
Secondary To define an expert standard when performing a primary elective THR. To determine if operative surgeon performance metrics during a THR relate to surgical experience, or patient outcomes.	Participants: 
 Wireless motion data metrics from elbow worn sensors (hand movements, path length and time taken) Patients: 
 X-ray analysis of THR.[4] Blood loss and transfusion rates. Peri-operative patient morbidity In-patient length of stay. PROMs: EQ-5D and OHS. 	Intra-operative assessments at a minimum of 5 separate THR operations for each participant in Group 2 (Experts & Fellows). Outcome measures data will be collected for all patients who have had a THR performed by any participant as the lead surgeon.

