9.3. Subsequent Visits

Group 1a ('StR's') - Intervention group:

StR's randomised to the 'intervention group' will be required to complete the 4-week period of additional training outlined in section 9.3. Following completion of this additional training, participants within this group will undertake approximately 2 intra-operative assessments every 6 weeks over the duration of their 6-month clinical placements (total 8 assessments). The StR's will also undertake a final Technical Skills assessment in OOSEC Laboratory at 3 months into their placement (See Appendix A for Study Flow Diagram).

Group 1b ('StR's') – control group:

Participants within this group will undertake approximately 2 intra-operative assessments every 6 weeks over the duration of their 6-month clinical placements (total 8 assessments). The StR's will also undertake a final Technical Skills assessment in OOSEC Laboratory at 3 months into their placement (See Appendix A for Study Flow Diagram).

Group 2: 'Experts' and 'Fellows':

Following enrolment for participation in this study, all participants within this group will undergo a baseline practical skills assessment within the OOSEC. Participants within this group will then undertake a minimum of 5 separate intra-operative assessments each.

Patients:

Following enrolment for participation in this study, all patients will be asked to complete the pre-operative PROMs questionnaires (EQ-5D and OHS). These are part of routine clinical care, and are a mandatory for all patients undergoing THR in the NHS. The patients will not be asked to undertake any further assessments outside of their routine clinical care until the time of their scheduled post-operative out-patient department (OPD) clinic review appointment. All patients will only be followed up routinely following discharge by their named Consultant in an OPD clinic. This OPD appointment normally takes place 6 to 8 weeks following discharge. No additional clinic appointments or investigations will be required outside of the patients expected routine clinical care. At this visit the patients will be asked to complete the post-operative validated PROMs questionnaires (EQ-5D and OHS). This takes a few minutes and is the only extra outcome measure the patients are asked to complete.

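### The number of Consultant and Fellow operations depends on an undefined reliability of the observed data, and the counts for StRs and patients are stated inconsistently.

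*Combined protocol and SAP*

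**What the plan says.** **Group 2 (Consultants and Fellows).** Section 7: "Both the 'Fellows' and 'Experts' will be assessed at a minimum of 5 separate THR operations depending upon the reliability of their performance data". Section 9.3 repeats the floor without the condition: "Participants within this group will then undertake a minimum of 5 separate intra-operative assessments each". The Synopsis and the section 6 table also give a minimum of 5. The Synopsis sample size nevertheless uses exactly 5 patients per Fellow and 5 per Consultant. Section 5 justifies combining the two because they have the same assessments on the same schedule, and section 7 itself promises set timepoints.

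**StRs.** Section 6: "Intra-operative assessments to be performed at a minimum of 8 separate THR operations for each participant in Group 1". Section 7: "Each StR enrolled into this study will be assessed at a minimum of 8 separate THR operations over a 6-month period". Section 9.3, for both arms: "approximately 2 intra-operative assessments every 6 weeks over the duration of their 6-month clinical placements (total 8 assessments". The Synopsis plans 8 patients per StR.

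**Patients.** Section 2: "Patient-specific outcome measures will be collected for a pre-determined number of patients". Section 6, and the Synopsis in the same terms: "Outcome measures data will be collected for all patients who have had a THR performed by any participant" as lead surgeon.

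**Analysis and conduct.** Section 11 compares StRs with Experts and Fellows, and the two StR arms, by Mann-Whitney. It does not say whether the unit is the operation or the surgeon. Section 9.7 has the PI collecting motion data in theatre and asks the PI not to reveal the StR's arm, which implies that the PI knows it. Section 9.5 says assessors will be blinded.

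**The concern.** For Group 2 the amount of data per surgeon is made to depend on the data themselves. Those data define the expert benchmark and form one side of the StR v Group 2 test. If variable surgeons are recorded more often and operations are pooled, they count for more and the benchmark looks more spread out than the group is. If recording instead stops once a surgeon's data look steady, the within-surgeon spread can be understated.

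For StRs the problem is different. With a floor in some sections and a total in another, nothing fixes which operations enter the randomised comparison. Section 9.7 stops recording when a Consultant takes over completely, but no section says whether that case counts or is replaced. Sections 13.5 and 13.6 provide neither monitoring nor an oversight committee that would pick up selective recording.

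**Working it through.** **1. The plan's own total.** Inputs from the Synopsis: 16 StRs × 8 + 8 Fellows × 5 + 5 Consultants × 5 = 128 + 40 + 25 = 193. This reproduces exactly, but only if each minimum is treated as a fixed number.

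**2. Weight of one Group 2 surgeon if operations are pooled.** There are 13 surgeons. If 12 have 5 operations and one has m, that surgeon's share is m/(60 + m), and the Kish effective number of surgeons is (60 + m)²/(300 + m²).

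| m | Share | Effective surgeons |
|---|---|---|
| 5 | 5/65 = 7.7% | 13.0 |
| 10 | 10/70 = 14.3% | 12.3 |
| 20 | 20/80 = 25.0% | 9.1 |

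**3. Effect on the benchmark (illustrative).** The documents give no variances, so all inputs are assumed.
- *Rule A.* 13 surgeons with log-normal within-surgeon SD (sigma 0.4), extended from 5 to 10 operations when their sample SD is above the median. If variable surgeons are assumed slower (mean rising 0.5 per unit SD), the pooled mean moves from 0.04 to 0.08 SD units, against a run-to-run SD of about 0.15. With that link set to zero the mean does not move. The pooled SD rises by about 7% either way.
- *Rule B.* Stop when SE/mean falls to 0.08–0.12, with a cap of 20. Ten surgeons are steady (log-SD 0.15) and three erratic (log-SD 0.45). The erratic three hold 50% to 41% of operations instead of 3/13 = 23%. The pooled mean is about 2% too high; weighting surgeons equally brings it within about 0.3% of the true value.
- *Rule B, all surgeons equally variable (log-SD 0.25).* The observed within-surgeon SD is 0.85–0.88 of the true value, against 0.93 with a fixed 5.

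**4. Would fixed counts be enough?** Simulated type I error of Mann-Whitney for 8 v 8 StRs, at an assumed two-sided 5% level:

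| Assumed ICC | Operations pooled, 8 each | Operations pooled, 8–24 each | Surgeon means |
|---|---|---|---|
| 0.05 | 8.9% | 13.4% | 4.9–5.1% |
| 0.20 | 19.8% | 33.2% | 4.9% |
| 0.40 | 30.0% | 47.6% | 4.3–4.7% |

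Fixed counts reduce the error but do not remove it. The unit of analysis has to be settled as well.

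**5. StR schedule.** Two assessments per 6 weeks with a total of 8 needs 8/2 = 4 windows, or 24 weeks. Section 7 starts assessments 6 weeks into a 6-month (about 26-week) placement. That leaves about 20 weeks, or 20/6 = 3.3 windows and about 6.7 assessments. If assessments are to end with the placement, the windows need dates before a total of 8 can be fixed.

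**The case against.** The strongest reply is that the clause is a sensible intention loosely worded. Continuing until a benchmark measurement is precise enough is legitimate if the rule is pre-specified and capped, and reliability might mean sensor or recording quality. That stands as an alternative, but the plan gives no definition, threshold or cap, so it is not yet such a rule.

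Several stronger readings are tempting, and the documents do not support them.
- *A reader might infer that StR counts are open-ended and extended on results.* No section links the StR count to outcomes, and section 9.3 gives a total of 8 in both arms. The fault is inconsistency, which permits selection but does not plan it.
- *That erratic surgeons will certainly gain weight.* This follows only if operations are pooled, and section 11 gives no unit. That unreliable data prompt more operations is the natural reading of section 7, not its wording.
- *That the benchmark mean is pulled towards erratic or slow surgeons.* Under Rule A the shift disappears without an assumed link between variability and speed, and with the link it is small beside sampling noise. Under Rule B it is about 2%.
- *That an unblinded investigator chooses when to stop.* No section says who decides. Group 2 has no allocation to be blind to. For StRs, the PI's knowledge of the arm is an inference from section 9.7, in tension with section 9.5.
- *That the reliability clause biases the randomised comparison.* It applies to Group 2 only, so it touches the secondary objectives.

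**Conclusion.** The concern holds in a limited form. The Group 2 count is tied to observed data by an undefined, uncapped condition that conflicts with the fixed 5 behind the total of 193, with the set timepoints in section 7 and with the common schedule claimed in section 5. If operations are pooled, a surgeon doubled to 10 operations goes from 7.7% to 14.3% of the benchmark data. The spread of the benchmark and the non-randomised StR v Group 2 comparison would be distorted, by about 7% in pooled SD under Rule A. Any shift in the mean is small and rests on assumptions.

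Separately, the StR count and the patient data collection are each described in incompatible ways, which leaves room for selective recording in the randomised comparison. The variances, ICCs, stopping rules and 5% level used here are assumptions, because the documents state none of them. The change is worth making because it is cheap, not because a large bias has been shown.

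**What to change.** 1. Delete the reliability clause in section 7 and report reliability as a result.
2. Base the main analysis on a fixed set: the first 5 eligible THRs per Consultant or Fellow, and the first 2 eligible THRs in each 6-week period (total 8) per StR. Taking the StR operations by period, not as the first 8 in a row, keeps the spread over the placement that section 9.3 intends. State the dates of the four periods and reconcile them with the week-6 start in section 7.
3. Use any further operations only in a sensitivity analysis.
4. Log every eligible operation that was not recorded or was taken over, with the reason, and state whether a taken-over case counts towards the total.
5. Use the same counts, and one rule for which patients contribute outcomes, in section 2, the Synopsis and sections 6, 7 and 9.3.
6. In section 11, weight surgeons equally through surgeon-level summaries, or use a model with a surgeon random effect. Fixed counts alone do not correct pooled tests.

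The cost is wording, a log and a statement of the unit of analysis. The downside is that extra operations do not enter the main analysis.

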- 2) Define an expert standard when performing a primary elective THR. This information will be a useful 'benchmark' against which Surgical Trainees performance and competence can be measured.
- 3) Determine if operative surgeon performance metrics during a THR relate to surgical experience, or patient outcomes.

The justification for including an 'Expert' comparator group within our study is to establish a benchmark standard of the optimal surgical performance metrics for a primary THR, against which we can assess StR performance. Within this study we have combined the 'Experts' and 'Fellows' into a single group as all the participants within this group are post-CCT (certificate of completion of training) in Trauma & Orthopaedic Surgery, and will undertake the same assessments at the same time points. The 'Fellows' are eligible to apply for Consultant posts, and will therefore represent a sub-Consultant level of performance, which we anticipate to be higher than that of StR's, but potentially below that of an established Consultant. The reason we are recording performance data for both 'Experts' and 'Fellows', is that this will allow further sub-group analysis, which may identify differences in performance metrics or patient outcomes between these surgeons.

The simulation-based training (intervention) to be tested in this study has been granted ethical approval by the University of Oxford Medical Sciences Interdivisional Research Ethics Committee (Reference MS-IDREC R57808/RE001).

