8.2. Patients

Adult patients (aged 18 years or above) diagnosed with primary hip osteoarthritis who have been listed for elective primary THR in the NHS.

Inclusion Criteria

- Adult patients (aged 18 years or above) diagnosed with primary hip osteoarthritis who have been listed for elective primary THR in the NHS.
- THR operation performed by a surgeon participant as lead surgeon.

Exclusion Criteria

Patients may not enter the study if ANY of the following apply:

- Patients with complex hip pathology (e.g. previous trauma, hip dysplasia, infection).
- Patients who have had previous surgery on their affected hip.

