9.7 Intra-operative surgeon performance data collection

The following protocol will apply to all episodes of intra-operative performance data collection for StR's and Fellows. The intra-operative data collection for Consultant performed operations will differ slightly in that they require no supervision, and no surgeon will 'take over' the operation. However, the methods for recording the intra-operative data will remain the same.

A maximum of two study participants (excluding Consultants) will attend any given list. The PI ([name]) will attend the World Health Organisation (WHO) briefing in theatre on the morning of the list, introduce themselves and explain their role during the list. If recording an StR, neither the participant or PI will disclose which arm of the study the participants are in (routine training, or additional simulation training). The supervising Consultant will confirm the cases on the list the StR or AF's will be performing under supervision and training.

Operative protocol

After anaesthesia and patient set-up, the supervising Consultant and participant will scrub in up in the usual manner with the motion sensors in position on the lead surgeon's elbows under their sterile gown (see Appendix C). The procedure will then continue routinely and normally, but with the PI collecting motion data via the wireless Bluetooth sensors. The PI will also manually record the timings of each stage of the THR operation. This process will allow synchronisation of motion data to the participants progression throughout the stages of the operation. Data collection will stop when the dressing has been applied to the surgical wound.

Following completion of the operation, the participants in conjunction with the supervising Consultant will be asked to complete short written assessments of the lead surgeons' intra-operative performance. These assessments may include: Global Rating Scales (GRS), Objective Structured Assessment of Technical Skills (OSATS), and surgical checklists.

Intra-operative deviations or interruptions

Sometimes the supervising Consultant needs to take over part or all of an operation if it proves particularly difficult. In the event that a procedure has to be taken over completely by the Consultant then data recording will stop. If minor adjustments only are made by the Consultant during the operation then these will be noted and time marked against the motion data.

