11 STATISTICS AND ANALYSIS

Analysis of motion data.

Motion data from the wireless sensors produces performance surrogate markers such as: the number of movements (major & minor); total path length; and smoothness/economy of movement. Data distributions will be assessed for normality using the Shapiro-Wilk test. Previous studies show such data are not normally distributed, and we would expect to use non-parametric tests, such as the Mann-Whitney U test to compare the performance metrics between the 2 groups of participants (StR's against Experts & Fellows). The Mann-Whitney U test will also be used to compare performance metrics between the two sub-groups of StR's (control and intervention), and also within the intervention sub-group in order to compare performance before and after training.

Performance metrics within all groups of participants will be reported using descriptive statistics to outline the central tendency (mean, median, and mode) and variation (range, variance, and standard deviation) in readings obtained. The Kruskal-Wallis one-way analysis of variance (ANOVA) test will be used to test for differences in the mean values obtained for all performance metrics between the two groups of participants. The Wilcoxon signed-rank test will be used to determine any differences in performance metric between the two groups.

Analysis of other routinely obtained data

X-ray (radiograph) analysis:

X-rays will be reviewed by two independent Consultant Orthopaedic Surgeons who will be blinded to the patient and lead surgeon's identity in order to reduce bias. There are several important parameters to be evaluated when reviewing a pelvic x-ray, therefore we will ask each reviewer to allocate a categorical global rating (see below) for both the pre- and post-operative x-rays. [5] The Chi-squared test will be used

to determine if there are any significant differences between each group, and also intra-group differences (for example StR's before and after additional training).

Pre-operative x-ray

- 1: Hip osteoarthritis without significant bone loss.
- 2a: Hip osteoarthritis with significant bone loss on acetabular side.
- 2b: Hip osteoarthritis with significant bone loss on femoral side.
- 3: Hip osteoarthritis with significant bone loss on both acetabular and femoral sides.

Post-operative x-ray

- 1: Excellent implant position and restoration of hip anatomy.
- 2a): Good overall with minor imperfections on acetabular side.

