12 DATA MANAGEMENT

Within this study both patients and participants will have all of their personal data anonymised via the use of Unique Patient or Participant Identifiers (UPI's). A master list of key linking identifiers for both patients

and participants will be kept on a password protected file on the OUH secure Trust Network Server. Only completely anonymised data will be used outside of OUH Trust property, which will be kept on a password-protected University owned laptop or hard-drive. We plan on keeping study data for a period of 5 years following completion on the study (up to December 2026), before securely disposing of it. We believe that this storage is appropriate as the core content is scientific research data and is therefore in the public interest. Furthermore, we will require access to this data in the case of individuals wishing to scrutinise the scientific methodology, results, or conclusions of our study.

Intra-Operative Data

Raw data will be produced from the wireless sensors. Please see section 12.3 for further details regarding the recording, transfer, and storage of this data.

Other 'personal data'

1) Electronic Patient Record Data

The following data will be obtained from the NHS Electronic Patient Records (EPR), which includes the Insignia Picture Archiving and Communication System (PACS), and the Theatre Management System (TMS):

- X-ray (radiograph) analysis.
- Theatre time usage.
- Blood test & transfusion rate analysis.
- Peri-operative morbidity (30 day).
- In-patient length of stay.
- Patient demographics (age, gender, BMI)

2) Questionnaire Data

Patient Questionnaire Data

The patient questionnaires consist of the following components:

- Patient Reported Outcome Measures: The OHS and EQ-5D.

Participant (Medical Health Professionals) Questionnaire Data

Written assessments of intra-operative performance will be conducted shortly after completion of a recorded THR. These assessments may include: Global Rating Scales (GRS), Objective Structured Assessment of Technical Skills (OSATS), and surgical checklists. The data collected from these will be anonymised as it will be linked with the UPI, and not provide any names or other personal information. The hard copies will be transcribed into digital format as soon as possible, which will be stored onto a password protected encrypted file on a University owned computer/hard-drive. The hard copies of the forms will then be disposed of.

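### Fixation and surgical approach are neither fixed, listed for recording nor adjusted for, so the non-randomised StR v Experts & Fellows comparison and the single expert standard cannot separate experience from type of operation

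*Combined protocol and SAP*

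**What the plan says.** **Technique.** Section 7 states: "There will be no interventions or deviations from routine clinical practise regarding the pre-operative investigations or work-up, the operation itself". The operative protocol in section 9.7 agrees: "The procedure will then continue routinely and normally, but with the PI collecting motion data via the wireless Bluetooth sensors".

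**Eligibility.** Section 8.2 admits "Adult patients (aged 18 years or above) diagnosed with primary hip osteoarthritis who have been listed for elective primary THR in the NHS". It excludes "Patients with complex hip pathology (e.g. previous trauma, hip dysplasia, infection" and earlier surgery on the same hip. These rules limit diagnosis and difficulty, not fixation or approach.

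**Data.** Apart from outcomes and theatre time, the patient-record list in section 12 holds only "Patient demographics (age, gender, BMI" as case descriptors, and section 12.6 confines extraction to the minimum dataset already outlined. In theatre the PI records motion data, stage timings and minor adjustments by the Consultant (section 9.7).

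**Use.** The outcome in section 6 is "Wireless motion data metrics from elbow worn sensors (hand movements, path length and time taken". Section 5 gives the purpose of the comparator group as to "establish a benchmark standard of the optimal surgical performance metrics for a primary THR". Section 11 compares StRs with Experts & Fellows by Mann-Whitney, and adds for the randomised arms: "The Mann-Whitney U test will also be used to compare performance metrics between the two sub-groups of StR's (control and intervention". No covariate, stratum or restriction is named for any motion metric.

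**Source of the groups.** Section 8.1 takes Consultants from the NOC only, and StRs and Fellows from the NOC and WGH.

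**The concern.** Movements, path length and time accumulate over the whole procedure; recording stops only when the dressing is on. If two types of THR differ in their steps or waiting periods, their totals can differ with equally skilled surgeons.

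This matters most where randomisation gives no protection. StRs and Experts & Fellows are not randomised against each other and come from different site mixes, and the supervising Consultant confirms which cases a StR performs. A different mix of operation types could then appear as a difference in experience. The expert standard would be an average over an unreported mix, which is a poor yardstick for any single operation. In the randomised comparison of StRs, operation type can only add noise and chance imbalance.

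**Working it through.** **1. The plan's own figure.** The synopsis gives 16 StRs × 8 + 8 Fellows × 5 + 5 Consultants × 5 = 128 + 40 + 25 = 193 patients, which reproduces. The non-randomised comparison is therefore 16 v 13 surgeons (128 v 65 operations), and the randomised one 8 v 8 StRs. These are upper targets: section 8.1 allows 12–16 StRs and 6–8 Fellows. The plan states no alpha, power, effect size or SD.

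**2. Assumptions (not in the documents).** One value per surgeon, normal with SD 1. One operation type adds c = 0.5, 1 or 2 SD. Two-sided exact Mann-Whitney at 5%.

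**3. Non-randomised comparison, no skill difference, type constant within surgeon.** Spurious shift = (difference in share of the type) × c.

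| Share, StR v Expert & Fellow | c | Shift (SD) | False positives, unadjusted | With type in the model |
|---|---|---|---|---|
| 50% v 20% | 0.5 | 0.3 × 0.5 = 0.15 | 6–7% | about 5% |
| | 1 | 0.30 | 11% | about 5% |
| | 2 | 0.60 | 21–22% | about 5% |
| 70% v 30% | 0.5 | 0.4 × 0.5 = 0.20 | 7–8% | about 5% |
| | 1 | 0.40 | 15–16% | about 5% |
| | 2 | 0.80 | 33–34% | about 5% |

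The spread within a cell is the difference between repeated simulations. If single operations are tested instead (65 v 128) and type adds 0.25 to 1 operation-level SD, the rates are about 6–22% for a 20-point difference in share and 9–67% for 40 points. With equal shares the rate is about 5%.

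**4. Randomised comparison, true effect 1.5 SD, 50:50 mix.** Variance of a StR's value is 1 + 0.25c² if each StR does a single type, and 1 + 0.25c²/8 if type varies over that StR's 8 operations.

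| c | Single type per StR: effect in SDs | Power | Type varies within StR: effect in SDs | Power |
|---|---|---|---|---|
| 0 | 1.50 | 77% | 1.50 | 77% |
| 0.5 | 1.5/√1.0625 = 1.46 | 74–75% | 1.5/√1.0078 = 1.49 | 77% |
| 1 | 1.5/√1.25 = 1.34 | 67–68% | 1.5/√1.031 = 1.48 | 75–76% |
| 2 | 1.5/√2 = 1.06 | 46–47% | 1.5/√1.125 = 1.41 | 72–73% |

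With no true effect, the 8 v 8 test on one value per StR rejects in about 5% of trials at every c.

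**5. Price of adjustment at 8 v 8.** When type has no effect, one type covariate lowers power from about 80–81% (matching t-test) to 76–77%. Four covariates that are constant within StR (for example cup fixation, stem fixation, approach and BMI) lower it to about 63%. That is below the unadjusted Mann-Whitney at c = 0, 0.5 and 1, and better only at c = 2.

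**The case against.** The documents nowhere say that fixation or approach varies at these two hospitals, differs between Consultants, or alters movements, path length or time. That stands, and it makes every size above conditional. A reader might infer that the metrics do measure which THR was done; the text supports only that the plan could not tell.

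A reader might also infer that the primary randomised comparison is compromised. It is not. Allocation is random, section 9.4 aims for an even spread of both arms over the two sites, and type I error stays near 5%. A large power loss needs each StR to do a single type, which the documents do not state. One qualification: if single operations were tested as independent and type were constant within StR, false positives would reach about 6–20% for shifts of 0.25 to 1 operation-level SD. That comes from ignoring clustering by surgeon, a separate matter.

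There is partial mitigation. Complex cases are excluded, pre-operative bone loss is graded, and stage timings would permit stage-level comparison. Fixation could probably be recovered from post-operative X-rays or the implant data that section 5 says the NJR holds; approach is less certain. None of this is written into section 11 as a way of handling operation type. The Appendix A flow chart is not shown.

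**Conclusion.** The point holds for the secondary objectives: the StR v Experts & Fellows comparison and the expert standard have no protection against a different mix of operation types. If shares differ by 30 to 40 points and type shifts the metric by 0.5 to 2 SD, the false-positive rate at 16 v 13 is about 6–34% instead of 5%. If the mix is the same in both groups, or type does not affect the metrics, that comparison is unharmed. Both quantities are assumptions.

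For the randomised comparison, the documents do not support a claim of bias. Type is noise there: power of about 73–77% if it varies within StR, and about 47–74% only if every StR does a single type. This is an inexpensive improvement worth making before data collection, not a fault in the trial's main contrast.

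**What to change.** 1. **Record.** The PI, already in theatre timing stages, notes fixation and approach for each recorded operation; both are added to the section 12 list.
2. **Non-randomised comparison and standard.** In section 11, adjust the StR v Experts & Fellows comparison of motion metrics and time for operation type, or stratify by it. State the expert standard by type, or for a named type, and report the mix in each group.
3. **Randomised comparison.** Keep the planned test as the main analysis and report the mix by arm. Use at most one pre-specified operation-type covariate, in a supporting analysis. Do not fit fixation, approach and BMI together at 8 v 8, given the power loss shown above.

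**Cost.** A few fields per operation, a change of wording in sections 11 and 12, and about one degree of freedom (roughly 4 points of power against the matching t-test, in the supporting analysis only). No extra patients or visits, and no change to how operations are done.
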